### **1.2 Secondary Objectives**

Our primary objectives include assessing sensitivity and responsiveness of all study procedures and assessments. We will thus not consider any objectives to be primary or secondary.

## **2. BACKGROUND AND RATIONALE**

### **2.1 Background on Condition, Disease, or Other Primary Study Focus**

Policing is one of the most highly stressful occupations. Unpredictable exposures to violence, chronic stress, job dissatisfaction, and expectations for optimal performance lead to an intensive work environment. Stress-impaired law enforcement officers (LEOs) are more likely to be aggressive toward suspects and use excessive force. LEO occupational stress has also been linked to disproportionately high rates of depression and suicide, PTSD, burnout, and alcohol misuse. Collectively, stress inherent to policing exacts enormous personal, financial, and societal costs.

Bureau of Justice Statistics (<https://www.bjs.gov>) estimates 59.4 million U.S. residents age 16 or older had one or more face-to-face contacts with police in 2011 (most recent year data were available). Among them, an estimated 2.3 million experienced threat or use of force by police, and nearly 75% of those described it as excessive. Appropriate use of force in acutely stressful situations is an essential component to safe and successful policing. However, physiological stress responses to acute LEO critical incidents can influence behavior and impact the outcome of the incident.

Studies on human responses to stressful events demonstrate neuroendocrine markers play an important role in physiological reactivity to stress. Stress responsiveness is primarily regulated by two neuroendocrine axes: the sympathetic adrenomedullary (SAM) and hypothalamic-pituitary-adrenocortical (HPA) systems - distinct but interrelated systems designed to help the body mobilize resources to deal with psychosocial and physical challenges that can be measured across different time points (e.g., acute, awaking profiles, chronic). Acute psychological stress quickly activates the SAM axis, eliciting release of catecholamines such as

noradrenaline and adrenaline, resulting in elevation of heart rate (HR), blood pressure (BP) and salivary alpha amylase (sAA). Dysfunction within the SAM and HPA systems among distressed and/or chronically stressed populations is thoroughly documented, including in LEOs, and is indicated by exaggerated or blunted reactivity to stressors and/or prolonged recovery time.

Regular exposure to acute and chronic stressors, such as organizational challenges, and exposure to violence and potential harm, contribute to elevated rates of LEO mental illness. LEOs experience, on average, over three traumatic events for every six months of service, with annual PTSD prevalence rates as high as 19%, compared to an estimated 3.5% prevalence in U.S. adults. High trauma-exposed LEOs are more likely to discharge their firearm during critical incidents, report higher rates of job dissatisfaction and burnout than most other occupations, and burnout is associated with aggression and excessive use of force. LEOs have high rates of alcohol consumption and binge drinking, and deaths due to alcohol-related liver disease are twice that of the general population. LEOs who engage in hazardous drinking are four times more likely to commit physical violence against others. Rates of depression and suicide are up to three times higher than the general public, even with probable underreporting of LEO suicide.

## 2.2 Study Rationale

Programs targeting LEO stress often lack effectiveness, with a focus on post-incident intervention instead of prevention. Despite elevated rates of PTSD, burnout, alcohol consumption, alcohol-related death, and suicide, and the significant implications of compromised officers to the safety of the public, effective LEO trainings and interventions are still lacking. The majority of intervention research among LEOs has examined Critical Incident Stress Debriefing (CISD), described as, “a structured group story-telling process combined with practical information to normalize group member reactions to a critical incident...only used in the aftermath of a significant traumatic event.” (p. 36) However, authors of a Cochrane Review concluded, “there is no evidence that single session individual psychological debriefing is a useful treatment for the prevention of post-traumatic stress disorder after traumatic incidents.” (p. 2) Although some individual studies report positive effects on specific indices of LEO mental health, RCTs, systematic reviews, and meta-analyses have concluded CISD is ineffective and can have iatrogenic effects, exacerbating acute stress reactions among LEOs and other first responders. A recent meta-analysis examining effectiveness of stress reduction programs among LEOs found small effect sizes, and concluded that, “insufficient evidence exists to demonstrate the effectiveness of stress management interventions for reducing negative physiological, psychological or behavioral outcomes among police officers and recruits.” (p. 508)

Mindfulness-Based Resilience Training is an 8-week program combining training in standardized mindfulness practices targeting factors that facilitate resilience, CBT, and psychoeducation. It contains experiential and didactic exercises including body scan, sitting and walking meditation, mindful movement and discussions. To supplement in-session content and support practice between sessions, MBRT participants will use the Ilumivu app, which is programmed with exercises and monitoring software.

Preliminary evidence suggests mindfulness training (MT) is a promising approach for the specific risks, challenges and outcome patterns present in the LEO population. MT has strong empirical support in lab-based, clinical, and community-based research, evincing outcomes such as reduced violence and aggression, and improved biomarkers of SAM and HPA stress reactivity, including HR, BP, cortisol, and sAA. In a recent study, authors concluded salutary effects of MT may be *most* likely in high-stress populations, in which stress is known to affect onset or aggravation of poor mental and physical health outcomes. Authors hypothesized that MT might “reduce SAM- or HPA-axis reactivity (or normalize dysregulated stress signaling in these systems), and subsequently impact stress-related disease-specific biological processes.” (p. 405).

MT may regulate how the individual appraises stress, and increase secondary appraisals of approach-oriented coping resources, thus reducing stress reactivity. Recent meta-analyses support this theory, indicating MT improves common LEO health and risk factors, including stress, depression and suicidal ideation, alcohol misuse, trauma, and burnout, and increases psychological resilience. MT has been shown to be feasible and to lead to improved health outcomes among several high-stress populations, such as military personnel, physicians, firefighters, and inner-city teachers. Resilience training has also been shown to improve the capacity to adapt to stress and improve outcomes in high-stress populations. These approaches often focus on skills training to buffer against ongoing acute and chronic stressors. Several pilot studies have shown LEO resilience-enhancing programs improve HR, BP, sAA and behavioral performance in live or simulated critical incident simulation tasks. Based on work with military and first-responder populations, Jha and colleagues recently proposed a conceptual model of risk reduction among high-stress professions, in which mindfulness and resilience synergistically impact health and risk factors, such as those common among LEOs.

Stress Management Education (SME) was designed as an active control condition for other Mindfulness-Based Intervention trials. SME uses a group-based didactic approach with modules on physiological and dietary effects of stress, time management, sleep physiology and insomnia, nutrition, exercise, stress hardiness, and factors mitigating impacts of stress. To supplement in-session content, and to match amount and format of assigned homework in the MBRT condition, SME participants will also use the Ilumivu app, programmed with audio content and monitoring software.

### **3. STUDY DESIGN**

The study will use an Individually-Randomized Group Treatment (IRGT) design, which will entail randomizing individuals, not groups, to an intervention that will be delivered to groups of Law Enforcement Officers (LEOs). An IRGT design is typically used when examining an intervention that is intended to be delivered to individuals or implemented at an individual level versus a Group/Cluster-randomized (GR) design that is used when the intervention is intended to be delivered and implemented at a group level. MBRT is delivered as a group, but the meditation practice is implemented at an individual level. Therefore, an IRGT design is preferable over a GR design, which is consistent with the use of an IGRT design in randomized controlled trials (RCTs) examining the efficacy of mindfulness-based interventions in the extant literature. An IRGT design will allow us to assess the impact of MBRT on individual LEOs.

The units of assignment and observation in the proposed study will be at the individual level since MBRT randomization and measurement will occur at an individual LEO level. Given that our primary objectives include assessing the sensitivity and responsiveness of all self-report, physiological, and behavioral outcomes, we will not consider any of our outcome measures to be primary or secondary measures. Our goal is to identify which outcomes are most impacted by MBRT, which will guide us in choosing primary and secondary outcomes in a future fully-powered efficacy RCT.

The target population for our study is LEOs working in urban settings in the United States. LEOs will be recruited from Portland Police Bureau (PPB), Albuquerque Police Bureau (APB), and Madison Police Department (MPD). PPB employs 966 full-time, active duty officers, serving approximately 603,106 citizens in the Greater Portland Metropolitan Area; women and racial/ethnic minorities represent 16% and 16%, respectively. APD employs 921 full-time, active duty officers, serving approximately 907,301 citizens in the Greater Albuquerque Metropolitan Area; women and racial/ethnic minorities represent 16% and 47%, respectively. MPD employs 486 full-time, active duty officers, serving approximately 258,054 citizens in the Greater Madison Metropolitan Area; women and racial/ethnic minorities represent 28% and 21%, respectively. We will make concerted efforts to recruit a target final sample comprising  $\geq 16\%$  women and  $\geq 16\%$  racial/ethnic minorities in Portland,  $\geq 16\%$  women and  $\geq 35\%$  racial/ethnic minorities in Albuquerque,  $\geq 25\%$  women and  $\geq 20\%$  racial/ethnic minorities in Madison.

We will recruit 104 participants. Using a 2:1.5:1 randomization allocation ratio for MBRT, SME, and NIC conditions, respectively, across the three study sites, 47 participants will be randomized to MBRT; 35 to SME; and 22 to NIC. Our sample size is based on feasibility trial recommendations suggesting 12-25 participants per arm to optimize estimation of group means and variability without oversampling in terms of diminishing returns in parameter estimation, and to provide reasonably precise information in terms of confidence intervals around retention rates.

If we do not get an adequate response from either of the two departments, we will expand recruitment to neighboring police departments in the Greater Portland Metro and/or Albuquerque Metro areas.

All data collection will happen remotely, either online or via home-based collection and mail (for dried blood spot samples).

The MBRT and SME interventions will remain time-matched, each totaling 17 hours over the 8-week delivery. However, the SME intervention sessions will be administered entirely online, aligned with standard usual care format for similar officer trainings. A preferred hybrid in-person/online format for MBRT will be implemented if safety guidelines permit, in which the 2 extended sessions (weeks 1 and 7) will be conducted in person, while other sessions will remain online. In-person sessions will take the following precautions:

- PPE face covering required by participants and research staff
- Only 50% room occupancy
- Temperature checks at the door, confirmation participant has no symptoms and is not part of a vulnerable population

If respective COVID-19-related state, local, or university policies prohibit or strongly recommend against in-person contact, all MBRT sessions will be administered entirely online. The hybrid vs. fully online format will be determined prior to engaging officers in the screening process, and will remain in place for the duration of that cohort. If state, local or university COVID-19-related recommendations or policies change during the course of a hybrid model, and session 1 has already been conducted in-person, session 7 may shift to an online format. The material and structure of the MBRT course allows for this flexibility.

At the Oregon study site, in-person MBRT intervention sessions would take place in the Pacific University Health and Resilience Center (PU-HRC) in Portland, OR. The building has four individual offices, two psychophysiology assessment rooms, a large conference/intervention room, and a space for secure storage of data. Drs. [name] and [name], and study coordinator [name] each have dedicated individual offices in this building and their Research Assistants have continuous and protected access to these offices along with dedicated student space.

At the New Mexico study site, in-person intervention sessions would take place at The Department of Psychology at the University of New Mexico (UNM).

Intervention locations at both study sites were carefully chosen, in collaboration with the corresponding police departments, to ensure low threshold accessibility. Per police department-recommended criteria, locations are central, accessible via public transportation, have parking options, and do not have signage that indicates mental health or addiction services, which can be a barrier for law enforcement participation. Space allows for compliance with social distancing recommendations.

Enrollment for the study will take place during Year Two of the grant from Month 2 through Month 8. The first phase of baseline data collection will occur during Month 4 of Year 2, directly preceding the beginning of MBRT and SME training for the first cohort of participants in Months 4 and 5. The second phase of baseline data collection is delayed due to COVID-19 restrictions. It will now occur during Year Three in Month 1, directly preceding the beginning of MBRT and SME training for the second cohort of participants in Months 2 and 3.

The first phase of post-intervention data collection will occur during Year 2, Month 8, directly following the end of the scheduled MBRT and SME training for the first cohort of participants; the second phase of post-intervention data collection will occur in Year 3, Months 3-4, directly following completion of MBRT and SME training for the second cohort of participants. Qualitative data collection (i.e., individual feedback interviews) for each training cohort will occur during the same months as post-intervention data collection.

The first phase of 3-month follow-up data collection (first training cohort) will occur during Year 2 Month 10; the second phase of 3-month follow-up data collection (second training cohort) will occur during Year 3, Month 6. The first phase of 6-month follow-up data collection (first training cohort) will occur during the Year 3, Month 2; the second phase of 6-month follow-up data

collection (second training cohort) will occur during the Year 3, Month 9. The first phase of 12-month follow-up data collection (first training cohort) will occur during Year 3, Month 8; the second phase of 12-month follow-up data collection (second training cohort) will occur during the Year 4, Month 1.

MBRT will be delivered in 8 weekly 1-hour sessions with an extended 7-hour class in week 1, and 4-hour class in week 7. MBRT contains experiential and didactic exercises including body scan, sitting and walking meditation, mindful movement and discussions. We have developed and refined MBRT based on focus group data from pilot research and feedback from our R21 trial (R21AT008854); content and language has been altered to be more relevant to LEOs, and there is greater emphasis on managing stressors inherent to police work, including critical incidents, job dissatisfaction, public scrutiny, and interpersonal, affective, and behavioral challenges. To supplement in-session content and support practice between sessions, MBRT participants will use Ilumivu mobile software, which is programmed with exercises and monitoring software. MPI [name] will co-lead the MBRT intervention with Co-I [name] (ret.) for all study sites. Co-Is [name] and [name] will collaborate with [name] to prepare for the training at the Oregon study site; [name], [name], and [name] will oversee MBRT interventionist training at the New Mexico study site. [name] co-developed MBRT, and is an expert in MBIs with first responders; [name] and [name] have facilitated, trained and supervised MBIs, and have collaborated on multiple MBI-related NIH trials.

Our active control group will be a Stress Management Education (SME) training, which is designed as an active control condition for MBSR trials. SME uses a group-based didactic approach with modules on physiological and dietary effects of stress, time management, sleep physiology and insomnia, nutrition, exercise, stress hardiness, and factors mitigating impacts of stress. It is an 8-week, 1.5-hour class with weekly homework (amount matched to MBRT), with 2 extended 4-hour sessions, and gentle movement exercises. [name] (SME developer) will provide input and support to ensure interventionists are trained to fidelity. Training will be conducted by trainers approved by [name], who has experience conducting SME and training interventionists. MPI [name], a licensed clinical psychologist with experience facilitating stress management groups, will oversee SME training with support from [name].

MBRT and SME groups will be led by separate interventionists, with at least masters level training in mental health or a related field, and matched for level of education and experience. MBRT interventionists will have previous training in and experience with MBRT or related interventions (e.g., MBSR, MBCT or MBRP), and will undergo intensive training, weekly clinical supervision, and regular meetings with MPIs to discuss fidelity and other clinical issues. Drs. [name], [name], and [name] are clinical psychologists with combined knowledge of psychoeducational protocols, MBIs, first responder populations, trauma, substance abuse, and other psychosocial outcomes. Given the importance of internal validity of interventions in RCT research, careful attention will be given to intervention adherence and consistency across sites, with all sessions being audio and video recorded. Under the supervision of [name], [name], and consultant [name], advanced graduate students at both study sites will review four randomly selected sessions from each MBRT cohort to assess intervention fidelity, adapting the MBRP Adherence and Competence measure used in previous trials. Drs. [name], [name], and [name], as well as consultant [name], will do the same for each SME cohort. Drs.

[name], [name] and [name] will provide weekly supervision to all interventionists to ensure fidelity and minimize drift. Participants in the NIC condition will not engage in a training; therefore, the administration of this group will only entail scheduling and meeting NIC participants for data collection.

Following baseline assessment, study staff not involved in data collection will randomly assign participants to a condition using SPSS and REDCap, stratifying for gender and using a permuted-block randomization procedure frequently used in mindfulness-based treatment trials to ensure balance within strata and across arms. The study statistician will create an allocation table using SPSS and upload it to REDCap, which study staff will use to implement the randomization procedure. Participants will be randomly assigned using a 2:1.5:1 ratio respectively (MBRT = 47; SME = 35; NIC = 22). Randomization will occur separately at each site to ensure equal ratios at all sites across the three trial arms. Since we are randomizing at each study site and stratifying for gender, study site and gender will become non-ignorable clusters. Therefore, we will adjust for study site and gender in our statistical models to avoid a deviation in our type I error rate from .05. We will include study site as a covariate in our statistical models. In addition, since including gender and study site as covariates in our statistical models will effectively decrease the sample size even further, we will conduct sensitivity and responsiveness to change analyses with and without covariates to ensure all inferential analyses can be conducted, and will compare the results between models with and without covariates to identify potential Type II Errors in models with covariates included.

Blinding will not be able to occur for participants since they will know their group assignment upon completing baseline assessment. We will, however, compartmentalize study staff to particular tasks and blind them to all other study components. Study staff will be involved in one of the following categories of activities and will not be involved in activities in any other category: design and analysis (i.e., designing the trial, overseeing design implementation, and analyzing trial data), intervention implementation (i.e., interventionist training, intervention implementation, and intervention fidelity monitoring), enrollment and randomization (using REDCap to randomize participants to trial arms and informing participants of their group assignment), recruitment (implementing recruitment, tracking participant enrollment and demographic information, maintaining contact with participants to schedule data collection appointments), and data collection (quantitative and qualitative data collection). Only study staff involved in enrollment and randomization activities will have access to both participant names and unique ID codes. This compartmentalization will create blinding for study staff in that those designing the trial and analyzing data will not be interacting with participants, involved in trial interventions, or have access to participant names; study staff interacting with participants in the interventions will not be involved in collecting or analyzing outcome data and will not have access to unique ID codes; study staff involved in data collection will be blinded to participant group assignment; study staff involved in collecting quantitative data will be blinded to participant group assignment as well as participant names (study staff involved in quantitative data collection will have access to unique ID codes); and study staff involved in qualitative data collection will be blinded to unique ID codes. (Due to the need to obtain qualitative information about participants' experiences in the SME and MBRT arms, we are unable to blind study staff involved in qualitative data collection to group assignment).

The study procedures (training, recruiting, randomization, etc.) will be overseen by the PU and UNM study sites. Overall design and direction of the protocol will reside in Oregon, and dried blood spot samples will be assayed at the Laboratory for Human Biology Research at Northwestern University under the direction of [name].

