### **6.2.2 Enrollment, Baseline, and/or Randomization**

#### **Enrollment**

Consent for study enrollment:

The study enrollment date is the day an individual who has met all the screening criteria signs (via REDCap) the informed consent form. A Randomization and Enrollment Form, documenting enrollment and allowable window between the enrollment date and randomization, will be entered into REDCap, a secure internet-based survey and data management software system housed on a secure server.

Randomization, immediately following completion of the baseline assessment procedure, must occur within 60 days of screening.

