#### **6.2.4 Followup Visits**

Postcourse followup (must occur within 21 days of end of 8-week intervention period).

- Proinflammatory Cytokines (C-RP, IL-6, IL-10, TNF- $\alpha$ )
  - Dried Blood Spot Collection Kit
- Psychological Resilience
  - Brief Resilience Scale
- Alcohol Misuse
  - PROMIS Alcohol Use
  - PROMIS Alcohol Use Negative Consequences
- Depression
  - PROMIS Depression
- Sleep Disturbance
  - PROMIS Sleep Disturbance
- Mindfulness
  - Five Facet Mindfulness Questionnaire – Short Form
- Self-Compassion
  - Self-Compassion Scale – Short Form
- Aggression
  - Buss Perry Aggression Questionnaire – Short Form
- Suicidal Ideation
  - Concise Health Risk Tracking - Self-Report
- Trauma Symptoms
  - PTSD Checklist for DSM-5
- Burnout
  - Oldenburg Burnout Inventory
- Sustained Attention to Response Task
- Interoceptive Awareness
  - Multidimensional Assessment of Interoceptive Awareness-II
- Perceived Stress
  - Perceived Stress Scale-10
- Global Impression of Change

- Acceptability
  - Acceptability of Assessment Procedures
  - Postcourse Satisfaction Survey (MBRT and SME)
- Intervention Compliance
  - Meditation Practice Questionnaire (MBRT)
  - Ilumivu (MBRT and SME)

3- and 6-month follow-up (must occur within  $\pm 10$  days of target date. Target date is relative to end of the intervention period, i.e., 90 days for 3-month followup, and 180 days for 6-month followup):

*Note: 6-month follow-up is final study visit.*

- Proinflammatory Cytokines (C-RP, IL-6, IL-10, TNF- $\alpha$ ) (**Only at 3-month follow-up**)
  - Dried Blood Spot Collection Kit
- Psychological Resilience
  - Brief Resilience Scale
- Alcohol Misuse
  - PROMIS Alcohol Use
  - PROMIS Alcohol Use Negative Consequences
- Depression
  - PROMIS Depression
- Sleep Disturbance
  - PROMIS Sleep Disturbance
- Mindfulness
  - Five Facet Mindfulness Questionnaire – Short Form
- Self-Compassion
  - Self-Compassion Scale – Short Form
- Aggression
  - Buss Perry Aggression Questionnaire – Short Form
- Suicidal Ideation
  - Concise Health Risk Tracking - Self-Report
- Trauma Symptoms
  - PTSD Checklist for DSM-5
- Burnout
  - Oldenburg Burnout Inventory

- Sustained Attention to Response Task
- Interoceptive Awareness
  - Multidimensional Assessment of Interoceptive Awareness-II
- Perceived Stress
  - Perceived Stress Scale-10
- Intervention Compliance
  - Meditation Practice Questionnaire (MBRT)
  - Ilumivu (MBRT and SME)

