12-month Followup (must occur on target date, which is 360 days from the end of the intervention period):

- Excessive Use of Force (Individual-level LEO excessive use of force (i.e., aggressive drawing and discharge of weapons, vehicle rams, illegal takedowns, administrative and citizen complaints)
  - BlueTeam^96 Database and/or other departmental data

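### The Section 3 calendar places cohort 2's 12-month use-of-force collection about two months before day 360, and its cohort 1 and enrollment months cannot all meet the Section 6.2 windows

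*Combined protocol and SAP*

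**What the plan says.** Section 3 assigns a grant month to every collection.

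- **Cohort 1.** Baseline is in Year 2 Month 4, "directly preceding the beginning of MBRT and SME training for the first cohort of participants in Months 4 and 5". Then: "The first phase of post-intervention data collection will occur during Year 2, Month 8". The 3-, 6- and 12-month collections are in Year 2 Month 10, Year 3 Month 2 and Year 3 Month 8.
- **Cohort 2.** After the COVID-19 delay, baseline is in Year 3 Month 1 and training in Year 3 Months 2 and 3. Post-intervention, 3-month and 6-month collections are in Year 3 Months 3-4, 6 and 9. Last, "the second phase of 12-month follow-up data collection (second training cohort) will occur during the Year 4, Month 1".
- **Enrollment.** "Enrollment for the study will take place during Year Two of the grant from Month 2 through Month 8".

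Section 6.2 times the same events from the end of the intervention. The post-course visit "must occur within 21 days of end of 8-week intervention period". The 3- and 6-month visits are due at 90 and 180 days, plus or minus 10. The 12-month collection "must occur on target date, which is 360 days from the end of the intervention period". Section 6.2.2 adds that randomization directly follows baseline and "must occur within 60 days of screening", and that the intervention starts 1 to 21 days later. Section 1.1 (Objective 2) allows one month to assemble the 12-month departmental data.

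**The concern.** The two sets of dates should agree, because Section 3 is the only place that turns the windows into collection months. They do not agree for cohort 2's 12-month collection, for cohort 1's visits, or for enrollment.

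Departmental use of force is the trial's only on-the-job behavioral measure. Under Section 1.1 it is assembled only before baseline and at 12 months, and Section 9.1 makes showing its usefulness as a research outcome an important objective. Section 9.6 analyzes individual indicators and a composite, and states no rate, offset or common observation length. If the collection follows the calendar, nothing in the analysis plan corrects for cohorts observed over different lengths of time.

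**Working it through.** Convention: a month is 365.25/12 = 30.44 days, and Month k runs from elapsed month k-1 to k. Eight weeks is 56 days, or 1.84 months; 360 days is 11.83 months.

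**Cohort 2, counted from the start of Year 3.** An eight-week course starting no earlier than Month 2 and finished within Month 3 ends between 1 + 1.84 = 2.84 and 3.00. The windows then give:

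- Post-course due in Months 3-4 (stated: 3-4), 3-month in Months 6-7 (stated: 6), 6-month in Months 9-10 (stated: 9). These three can be reproduced.
- 12-month: 2.84 + 11.83 = 14.67 to 3.00 + 11.83 = 14.83, which is Year 4 Month 3. Stated: Year 4 Month 1.
- Year 4 Month 1 spans 12 to 13. Distance from end of training: (12 - 3.00) × 30.44 = 274 days to (13 - 2.84) × 30.44 = 309 days. Shortfall: 360 - 309 = 51 to 360 - 274 = 86 days.

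If training only begins in Months 2-3, the distance is 218-309 days, which is no better.

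A second check needs no training date. The 6-month visit is in Year 3 Month 9 and may be at day 190 at the latest, so day 360 comes at least 170 days later. From the first day of Year 3 Month 9 to the last day of Year 4 Month 1 is 5 × 30.44 = 152 days. The two stated months cannot both comply.

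**Cohort 1, counted from the start of Year 2.** Two readings of "for the first cohort of participants in Months 4 and 5" are possible.

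- *Reading A: training occupies those months.* It ends between 3 + 1.84 = 4.84 and 5.00.
- *Reading B: training begins in those months.* Baseline is in Month 4, so with randomization at baseline and a start within 21 days (taken as counted from randomization), the latest start is day 21 of Month 5. Training then ends 21 + 56 = 77 days after the start of Month 5.

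| Collection | Stated month | Window (days) | A: days after training | B, latest start: days after training |
|---|---|---|---|---|
| Post-course | Year 2 Month 8 | 0-21 | 61-96 | 14-45 |
| 3-month | Year 2 Month 10 | 80-100 | 122-157 | 75-106 |
| 6-month | Year 3 Month 2 | 170-190 | 244-279 | 197-227 |
| 12-month | Year 3 Month 8 | 360 | 426-461 | 380-410 |

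For example, the 6-month entry under B starts at 9 × 30.44 - 77 = 197, and the 12-month entry at 15 × 30.44 - 77 = 380. Under A all four are late. Under B the post-course and 3-month visits can comply, but the 6- and 12-month dates still miss. Earlier starts only increase the distances.

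Working backwards, the 12-month month needs training to end at 19 - 11.83 = 7.17 or later. The 3-month month needs 10 - 80/30.44 = 7.37 or earlier. All four months therefore fit together only if training ended in early Month 8.

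**Enrollment.** From the end of Year 2 Month 8 to the start of Year 3 Month 1 is (12 - 8) × 30.44 = 122 days, against a limit of 60.

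**The case against.** The strongest defense is that Section 6.2.4 states the participant-level rule and Section 3 is only a planning calendar. If staff work from Section 6.2.4, the error stays on paper. That stands as a limit on the harm, but the two sections still contradict each other.

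A second defense is that cohort 2's date was counted from baseline: Year 3 Month 1 plus 12 months is Year 4 Month 1. That may be how it arose. But Section 6.2.4 counts from the end of the intervention, and cohort 1's date does not follow a baseline rule (Year 2 Month 4 plus 12 is Year 3 Month 4, not Month 8). The assembly allowance moves a collection later, not earlier.

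For cohort 1, the size of the miss depends on the reading. Without the 21-day start rule, a group starting in the last two or three days of Month 5 would meet the post-course, 3-month and 6-month windows, and its 12-month date would be 10 days past target. Under B the 20-day overrun at 12 months (380 - 360) fits inside the assembly month; the 6-month miss does not.

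A reader might infer four stronger things that the documents do not support:

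- *That the outcome is defined on days 0-360 and cohort 2 loses 14-24% of it.* Section 6.2.4 fixes when data are collected. No section defines the counting period, so lost exposure is an inference.
- *That exposure differs 1.4- to 1.7-fold between cohorts.* This takes cohort 1's training to end with Month 5. The visit months may be right and the training months wrong, and events after day 360 can be left out of a late collection.
- *That the arms are biased.* Randomization is within site and NIC assessments are yoked to the active arms (Section 5.1), so unequal follow-up falls on all arms alike. The trial also tests no efficacy hypothesis.
- *That cohort 2 cannot be randomized.* The enrollment sentence looks like text left unchanged when the baseline was delayed. Officers enrolled and screened near the new baseline would meet the 60-day rule.

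**Conclusion.** The contradiction is real. Cohort 2's 12-month collection is scheduled 51-86 days before its required date, two calendar months early, and no reading tried removes this. Cohort 1's training and collection months cannot all satisfy Section 6.2.4; how far they miss depends on what its training months mean. The enrollment period is out of date by at least 122 days against a 60-day rule.

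The consequence is conditional. If Section 3 is followed for collection, and use of force is counted up to the collection date, cohort 2 contributes about 9-10 months after training and cohort 1 about 12 or more. The pooled outcome is then noisier and less comparable across cohorts, without evident directional bias between arms. If Section 6.2.4 is followed, the problem is confined to the calendar text.

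The figures assume months of 30.44 days, an eight-week course, and a start within 21 days of randomization. The 14-day limit between baseline and intervention in the Précis is stricter and would only widen cohort 1's miss. The correction should be made: it concerns an operative collection date and costs almost nothing.

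**What to change.** Reconcile Section 3 with Sections 6.2.2 and 6.2.4:

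1. Move cohort 2's 12-month collection to Year 4 Month 3, with day 360 as the data cut-off and the one-month assembly allowance after it.
2. Correct either cohort 1's training months or its visit months, using the dates on which its intervention period actually ran.
3. Update the enrollment period so that it leads into the cohort 2 baseline and the 60-day limit can be met.
4. State in Section 9.5 or 9.6 that use of force is counted over the same fixed period for every officer, from the end of the cohort's intervention period to day 360. NIC officers have no sessions, so use the yoked date. If a collection has already been made early, repeat it; if late, drop events after day 360.

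The cost is protocol wording and one database collection moved by about two months, with no participant contact. The downside is that cohort 2's use-of-force data arrive about two months later than the calendar states. So does the offer of MBRT to cohort 2 SME and NIC officers, because Sections 4.3 and 6.2.2 place that offer after the final 12-month collection.
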